2.3 Summary of Nonclinical Studies with ABNCoV2 Vaccine

The immunogenicity of ABNCoV2 has been demonstrated in mice (Fougeroux et al., 2021) and in non-human primates (NHP). A single intramuscular (IM) administration of 100 µgABNCoV2 induced SARS-CoV-2 neutralizing antibodies in NHP at comparable levels as found in human convalescent samples, while neutralizing antibody titers induced by 15 µg ABNCoV2 remained below convalescent levels. A second administration of 15 or 100 µg ABNCoV2 led to a >50-fold increase in titers. While 15 µg ABNCoV2 administered 2-times to NHP resulted in significantly reduced lung viral load after SARS-CoV-2 challenge compared to nonvaccinated control animals, the higher dose of 100 µg ABNCoV2 administered 2-times was more effective in that the majority of animals were completely free of virus in lung and also in nasal swabs, demonstrating complete protection. Therefore, the high dose administered 2-times has been chosen to be evaluated in seronegative subjects in the phase 2 trial (a single high dose boost regimen will be administered to seropositive subjects).

The safety and good tolerability of 100 µg ABNCoV2 (adjuvanted in a squalene in water emulsion) administered 2- or 3-times in rabbits was shown in a Good Laboratory Practice (GLP) compliant repeat dose toxicity and local tolerance study, that did not raise any safety concerns for human use.

The ABNCoV2 dose administered to rabbits translates to a human equivalent dose based on body surface area (FDA, 2005) of 774 µg for a 60 kg human; this provides a safety margin of >7x higher than the 100 µg human dose. Even when taking into account an offset between laboratories using different reagents to determine the ABNCoV2 protein concentration, a potentially lower dose of 70 µg instead of 100 µg used in the toxicity study translates to a human equivalent dose of 542 µg for a 60 kg human and still provides a safety margin of >5x higher than the 100 µg human dose in this phase 2 trial. Further, the number of vaccine applications (3) was in excess of the 1-2 administrations planned in this phase 2 trial, thereby providing an additional safety margin.

See further details in the current effective ABNCoV2 IB.

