4.7 Early Discontinuation

Reasons for early discontinuations:

A subject may be discontinued from the trial early for different reasons. The decision to discontinue early can be made by the investigator or by the subject. Reasons for early discontinuation of a subject may include, but are not limited to:

- An AE/SAE/AESI that, in the opinion of the investigator, makes it unsafe for the subject to receive a vaccination
- Pregnancy
- An anaphylactic reaction following the administration of any vaccine(s)
- Clinical need for concomitant or ancillary therapy not permitted in the trial as outlined in [Section 8.8](#).
- Subject's receipt of an approved booster vaccination for SARS-CoV-2.
- Subject's request to discontinue (withdrawal of consent to participate).
- Subject unwilling or unable to comply with trial requirements.
- Any reason that, in the opinion of the investigator, requires or supports early discontinuation of a subject.

Handling of early discontinuations:

Each subject has the right to terminate their trial participation completely at any time for any reason, and the investigator may also terminate a subject's trial participation. Subjects whose trial participation is terminated during the active trial phase should undergo a concluding EAP visit, including safety laboratory testing and pregnancy test for WOCBP. The subject has the right to refuse the optional EAP visit, however, the CTS should make an effort to collect any safety data possible for the subject. If the subject consents, the 3-month FU visit (FU1) should still be performed to collect any potential SAEs/AESIs which occurred after the last vaccination. Subjects who discontinued after receiving trial vaccine will not be replaced.

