4.1.3 Study Periods and Windowing

The following study periods are defined for this trial:

Screening Period: The period from the subject's signing of informed consent to the trial through the date and time of first vaccination. AEs starting during this period are considered Baseline Signs and Symptoms.

Active Trial Period: The period from the first vaccination up to and including week 4 (28-35 days) after receiving their vaccination. A visit at the end of the Active Trial Period is scheduled per protocol. In the event of early withdrawal of a subject from the trial during the Active Trial Period, the EAP visit may occur prior to the 28-35 days post-last vaccination window. For the purpose of safety analyses, any safety information collected within 35 days of their vaccination received will be included in summaries of the Active Trial Period.

FU Period: The period from the EAP visit through the final follow up visit. Subjects have 3 FU visits at 4, 9 and 22 weeks after the scheduled EAP visit (Weeks 8, 13 and 26). Subjects may withdraw from treatment early but continue into the FU Period.

For assigning prior and concomitant medications, those ending prior to the first vaccination are considered prior medications. All other medications are considered concomitant medications.

For AEs and medications with partial or missing start and/or stop dates, the “worst case” should be applied to be conservative. Therefore, the following rules will apply:

AEs

- If start date is partial and any portion (i.e., year or month and year) would confirm the AE was prior to first vaccination, the AE will be considered a Baseline Sign or Symptom.
- If the start date is completely missing and the end date, or any portion of a partial end date, confirms the AE ended prior to first vaccination, the AE will be considered a Baseline Sign or Symptom.
- Otherwise, the AE will be considered as belonging to the Active Trial Period.

Medications

- If the end date is partial, and any portion confirms the medication was ended prior to first vaccination, the medication will be considered a Prior Medication.
- Otherwise, the medication will be considered a Concomitant Medication.

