4.2.3.2 Sensitivity using Multiple Imputation for the Safety Analysis Set

Because the window between vaccination and the primary endpoint measurement is short, the number of subjects with missing data due to intercurrent events or protocol deviations substantially affecting the immunogenicity results is expected to be small. If data are missing despite the short window, missing values will be imputed via the multiple imputation (MI) method as a sensitivity analysis using the Safety Analysis Set. Missing values will be assumed to be missing at random, such that the reason for the missing value is not dependent on the result itself. As the MI procedure will be performed on the Safety Analysis Set, regardless of protocol deviations, post vaccination neutralizing titers that are out of window will be included rather than imputing a “missing” value for full accounting of the available data. Inclusion of out of window titer results will follow the method used for the Sensitivity Analysis using the Safety Analysis Set.

The multiple imputation sensitivity analyses will be performed separately for each group due to the different background characteristic of the two populations. Although analyses for Groups 2 and 3 are based on the fold-increase from baseline neutralizing titers, imputation of missing data will be performed at the neutralizing titer level, with fold-increase computed after imputation.

Group 1 Multiple Imputation Procedure

For Group 1, assuming the post-vaccination \log_{10} titer values are normally distributed, MI will be used to create 100 complete data sets that will account for the random variability in the \log_{10} neutralizing titer values. Week 2, Week 4, and Week 5 \log_{10} neutralizing titer results, number of vaccinations received, year of birth, sex, and race will be used in the joint model to predict the \log_{10} neutralizing titer value for the primary estimand time point at Week 6.

Qualitative tests for SARS-CoV-2 antibodies are required for inclusion in the trial and appropriate placement of subjects into their respective seronegative or seropositive groups. As Group 1 subjects are required to be seronegative at screening, most Baseline neutralizing titers are expected to be below the LLOQ. As this would provide little information to the joint distribution from which to draw the MI samples, Baseline neutralizing titer values will not be included in the Group 1 MI procedure.

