In addition, as the missing pattern of titer values may not be monotone, i.e., subjects may be missing Week 2, Week 4, Week 5, or Week 6 neutralizing titer results, or a combination of these values, a fully conditional specification (FCS) method will be used. This method assumes the existence of a joint distribution for all variables used to predict the missing values and allows Week 2, Week 4, and Week 5 \log_{10} titer value to be imputed, if needed, to inform the missing Week 6 neutralizing titer values.

MI analyses will be performed in SAS using the PROC MI and PROC MIANALYZE procedures. A minimum of \log_{10} of half of the LLOQ will be set for imputed values to correspond to the observed data range. In addition, a seed of 19201 will be used for the procedure. The following is the sample code for the MI sensitivity analyses of the primary estimand for Group 1.

titersl: the dataset containing the \log_{10} neutralizing titer data along with the covariates used in the analysis, one record per subject.

sex: The sex identifier

yob: Year of birth

race: The race identifier

nvacc: Number of vaccinations received (1 vs. 2)

ltiterW2: \log_{10} Week 2 Titer Result

ltiterW4: \log_{10} Week 4 Titer Result

ltiterW5: \log_{10} Week 5 Titer Result

ltiterW6: \log_{10} Week 6 Titer Result

```

proc mi data=titersl out=titermi n impute=100 seed=19201 minimum=[log10LLOQ/2];
  class nvacc sex race;
  var nvacc yob sex race ltiterW2 ltiterW4 ltiterW5;
  fcs nbiter=20 reg(ltiterW6 = ltiterW2 ltiterW4 ltiterW5 nvacc yob sex race
    /details);
run;

proc means data=titermi n oprint nway;
  by _imputation_;
  var ltiterW6;
  output out=summ(drop=_type_ _freq_) n=n mean=logmn stderr=logse;
run;

ods output parameterestimates=grouplest;
proc mianalyze data=summ;
  modeleffects logmn;
  stderr logse;
run;
data grouplest2;
  set grouplest;
  GMT=10**estimate;
  GMT_LCL=10**LCLmean;
  GMT_UCL=10**UCLMean;
  keep estimate lclmean uclmean gmt:;
  label estimate='Mean Log10 Titers'
    lclmean='Lower 95% CI of the Mean Log10 Titers'
    uclmean='Upper 95% CI of the Mean Log10 Titers'
    gmt='Geometric Mean Titer'
    GMT_LCL='Lower 95% CI of the Geometric Mean Titer'
    GMT_UCL='Upper 95% CI of the Geometric Mean Titer'
run;

```

Groups 2 and 3 Multiple Imputation Procedure

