4.2.4 Supplementary Analyses

The primary analysis will be supported by descriptive summaries including medians, geometric means and corresponding 95% CIs, Min, and Max for each serum collection time point. These summaries will be performed for both the Immunogenicity Analysis Set and the Safety Analysis Set. No windowing or imputation will be applied for this summary, as they will be presented by the visit at which the serum sample was acquired.

A responder analysis will be performed, with response analyzed by serum collection time point. Response defined separately for naïve subjects (Group 1) and experienced subjects (Groups 2 and 3) as follows:

- Group 1: having SARS-CoV-2 neutralizing antibody titers above the LLOQ, or
- Groups 2 and 3: having an at least 2-fold, 4-fold, and/or 6-fold increase from baseline SARS-CoV-2 neutralizing antibodies.

For Group 1, subjects are required to have a negative qualitative SARS-CoV-2 test at screening to enter the trial. Despite this, there is a chance they have positive neutralizing titer at baseline. In this case, response would be defined as an at least 2-fold increase from baseline in neutralizing titer.

Response rates will be summarized for the Immunogenicity Analysis Set by time point as well as overall for the Active Trial Period, and corresponding 95% CIs will be calculated using the Clopper-Pearson method. The response rate analysis will also be repeated for the Safety Analysis Set with subjects missing a value for a time point, and not having achieved a response at a previous timepoint, counted as non-responders. For the final CSR, an over response rate will be calculated inclusive of the FU visits in addition to the Active Trial Period rates.

The primary analyses will also be performed within sex (male vs. female) and age groups as supportive analyses: 18 to < 50 years, 50 to < 65 years, 65 to < 75 years, and \geq 75 years. These summaries will be performed for the Immunogenicity Analysis Set only.

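### If every Group 1 subject who stops after dose 1 also leaves the trial, the multiple imputation gives them two-dose Week 6 titers, and unboosted early EAP sera enter the Week 8 summary

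*SAP*

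**What the plan says.** **After stopping.** Protocol 4.7 states: "Subjects whose trial participation is terminated during the active trial phase should undergo a concluding EAP visit". It adds that "The subject has the right to refuse the optional EAP visit", and that with consent "the 3-month FU visit (FU1) should still be performed to collect any potential SAEs/AESIs". It mentions no Week 5 or Week 6 visit for these subjects. SAP 4.1.3 lets subjects who withdraw from treatment early move into the follow-up period, and accepts that after early withdrawal "the EAP visit may occur prior to the 28-35 days post-last vaccination window".

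**Estimand.** Discontinuation due to AEs, from dose 2 or from the trial, is the second intercurrent event. The stated strategy is treatment policy (Protocol 9.9; SAP 1.1 and 4.2.1).

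**Imputation.** SAP 4.2.3.2 covers the Safety Analysis Set under missing at random. In Group 1, Week 2, 4 and 5 titers are predictors, and "number of vaccinations received, year of birth, sex, and race will be used in the joint model to predict the" Week 6 titer. The dose covariate is defined as "nvacc: Number of vaccinations received (1 vs. 2". Available out-of-window titers are used before anything is imputed, following the rule in SAP 4.2.3.1. That rule refers to values after the *last* vaccination, which SAP Appendix 1 defines for Group 1 as the second dose.

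**By-visit summaries.** SAP 4.2.4 summarises titers at each serum time point for both analysis sets: "No windowing or imputation will be applied for this summary, as they will be presented by the visit at which the serum sample was acquired". Both schedules mark serum at V7/EAP, target week 8, which is the Group 1 time point four weeks after the boost.

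**The concern.** The dose covariate is the plan's own device for keeping one-dose subjects apart from two-dose subjects. It works only if some one-dose subjects have a Week 6 titer, and the visit schedule for people who leave the trial makes that unlikely. Without such titers, the imputation answers what these subjects would have shown with dose 2. Treatment policy asks what they showed without it. A sensitivity analysis meant to account for everyone vaccinated would then tend to reproduce the two-dose result and look reassuring.

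The EAP problem runs the other way. A serum taken on withdrawal, before any second dose, carries the V7/EAP label and is averaged with genuine four-weeks-post-boost samples.

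**Working it through.** **1. The plan's own figure.** SAP section 6 gives SD 0.5 (log10), n = 30 and half-width 0.179. Check: 1.96 × 0.5/√30 = 0.1789. Back-transformed, this gives 132.5-302.0 around 200 and 165.6-377.4 around 250. The stated 132-302 and 166-377 are reproduced.

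**2. Can the dose effect be estimated?** If all one-dose subjects lack Week 5 and Week 6 sera, the number of vaccinations equals 2 in every row with an observed Week 6 titer. With predictors intercept, Week 2, Week 4, year of birth, sex and dose (race left out), the design for Week 5 has rank 5 of 6 columns. With Week 5 added, the design for Week 6 has rank 6 of 7. The dose coefficient is not identified. Missing at random does not help, because no one-dose Week 6 values are observed.

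**3. Size of the imputation effect.** Let F be the two-dose/one-dose titer ratio and m the number of such subjects among 30. If they are imputed at two-dose level, the GMT is inflated by F^(m/30), a shift of (m/30) × log10 F. Neither F in humans nor m is in the documents. F = 5, 10 and 50 are assumptions. The only figure given is from non-human primates, where a second dose "led to a >50-fold increase in titers" (Protocol 2.3).

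| m | F = 5 | F = 10 | F = 50 |
|---|---|---|---|
| 1 | 1.055 (0.023) | 1.080 (0.033) | 1.139 (0.057) |
| 2 | 1.113 (0.047) | 1.166 (0.067) | 1.298 (0.113) |
| 3 | 1.175 (0.070) | 1.259 (0.100) | 1.479 (0.170) |

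Log10 shifts are in brackets, for comparison with the half-width of 0.179.

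**4. Simulation.** Week 5 and then Week 6 were imputed by Bayesian regression (400 replicates, 20 imputations, SD 0.5, assumed correlation 0.5, two-dose GMT 200, one-dose GMT 200/F).

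| One-dose subjects | Observed at Weeks 5 and 6 | F | Imputed geometric mean | One-dose truth | MI GMT | True GMT |
|---|---|---|---|---|---|---|
| 3 | 0 | 5 | 193 | 40 | 198 | 169 |
| 3 | 0 | 10 | 199 | 20 | 200 | 160 |
| 3 | 0 | 50 | 203 | 4 | 201 | 137 |
| 4 | 2 | 10 | 20.7 | 20 | 145.3 | 145.6 |
| 4 | 2 | 50 | 4.3 | 4 | 121.0 | 120.5 |

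With no one-dose Week 6 data the covariate does nothing. With two observed one-dose subjects it works. The simulation was in Python with a minimum-norm solution for the singular fit, and SAS was not run. The Group 1 sample code also omits the Week 6 titer from its VAR list, so it needs checking before it shows what would be imputed.

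**5. Early EAP serum.** One unboosted sample among 30 at Week 8 multiplies that GMT by F^(-1/30): 0.948 (F = 5), 0.926 (F = 10), 0.878 (F = 50). The GMT falls by about 5%, 7% and 12%.

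**The case against.** A reader might infer that every subject who stops after dose 1 lacks a Week 6 sample. The documents do not support that. Protocol 8.18 lets a subject who becomes pregnant forgo further doses and continue other procedures, and the second intercurrent event separates stopping dose 2 from leaving the trial. Nor does the plan ignore dose, since the covariate is in the model. It would be wrong to conclude that the covariate should simply be dropped: step 4 shows it working when one-dose Week 6 values exist.

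The out-of-window rule has a second reading. SAP 4.2.3.2 speaks of titers *post vaccination*. Read alone, this could let an early EAP or FU1 serum stand in for Week 6, with nothing imputed. The section then defers to 4.2.3.1 and its *post-last vaccination* rule, so imputation is the better reading, but the wording is unsettled.

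The primary question in SAP 1.1 concerns titers after the protocol-specified regimen, and a two-dose imputation arguably fits it. It does not fit the treatment-policy label attached to discontinuation.

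On the EAP serum, SAP section 3 lists stopping before both doses as a possible exclusion from the Immunogenicity Analysis Set, and the visit can be refused. Contamination of the exploratory four-week post-boost endpoint is therefore possible, not certain. In Groups 2 and 3 an early EAP serum follows the only dose, so it is mistimed, not unboosted, and no size is claimed.

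Finally, the plan expects few missing values, tests no hypothesis, and reports Group 1 outside the analysis that informs phase 3 (SAP 4.6 and 4.7). All of that stands and limits the consequence.

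**Conclusion.** The point holds conditionally. If no one-dose Group 1 subject has an observed Week 6 titer, the dose effect is not estimable and the imputation draws two-dose values for subjects who never had dose 2. With n = 30 and an assumed 5- to 50-fold dose-2 effect, the imputed GMT is too high by about 6-14% for one such subject and 11-30% for two. An early, unboosted EAP serum that is collected enters Week 8 in the Safety Analysis Set summary, and in the Immunogenicity Analysis Set only if the subject is not excluded. Each such sample lowers that GMT by about 5-12%.

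A reader might infer that the primary Group 1 estimate is biased. It is not affected by the imputation, which is a sensitivity analysis. The by-visit table is descriptive. For one subject, the imputation shift of 0.023-0.057 log10 is well inside the planned half-width of 0.179. It approaches the half-width only at three subjects and 50-fold (0.170). The change is still worth making, because the rules as written can give wrong Group 1 values and the remedy is wording.

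**What to change.** 1. **SAP 4.2.3.2.** Keep the number-of-vaccinations covariate only when enough one-dose Week 6 titers are observed to estimate its effect, and state that condition. Otherwise impute one-dose subjects under no boost, from their own post-dose-1 titers (Week 2, Week 4, early EAP), with proper imputation variance. Align *post vaccination* with *post-last vaccination* in 4.2.3.1, so that it is clear whether one-dose sera can count as Week 6. Check the VAR list in the sample code at the same time.
2. **SAP 4.2.4.** Include EAP serum in the Week 8 (Group 1) or Week 4 (Groups 2 and 3) summaries only if it was drawn 28-35 days after the last scheduled dose was actually given. List other EAP sera by actual day.
3. **Optional, Protocol 4.7.** Invite subjects who stop vaccination but agree to remain in the trial to give the already scheduled V6 serum. From the stated windows this is (28 to 35) + (12 to 16) = 40 to 51 days after V1.

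Items 1 and 2 cost SAP wording and some programming. Item 3 costs one scheduled blood draw for a few subjects, plus a protocol wording change.

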As with Group 1, MI analyses will be performed in SAS using the PROC MI and PROC MIANALYZE procedures. A minimum of \log_{10} of half of the LLOQ will be set for imputed values to correspond to the observed data range. In addition, a seed of 19201 will be used for the procedure. The following is the sample code for the MI sensitivity analyses of the primary estimand for Groups 2 and 3.

titersl: the dataset containing the \log_{10} neutralizing titer data along with the covariates used in the analysis, one record per subject.

sex: The sex identifier

yob: Year of birth

race: The race identifier

stratgoup: Stratification subgroup (prior mRNA vaccine, prior Adenovirus-based vaccine, prior COVID-19 infection)

ltiterBL: Log₁₀ Baseline Titer Result

ltiterW1: Log₁₀ Week 1 Titer Result

ltiterW2: Log₁₀ Week 2 Titer Result

lfoldinc: Log₁₀ Fold Increase from Baseline to Week 2 Titer Result

```

proc mi data=titersl out=titermi n impute=100 seed=19201 minimum=[LLOQ/2];
  class stratgroup sex race;
  var stratgroup yob sex race ltiterBL ltiterW1;
  fcs nbiter=20 reg(ltiterW2 = ltiterBL ltiterW1 stratgroup yob sex race
    /details);
run;

data titersmi2;
  set titersmi;
  lfoldinc= ltiterW2 - ltiterBL;
run;

proc means data=titermi2 nointer nway;

```

```
by _imputation_;
var lfoldinc;
output out=summ(drop=_type_ _freq_) n=n mean=logmn stderr=logse;
run;

ods output parameterestimates=group2est;
proc mianalyze data=summ;
  modeleffects logmn;
  stderr logse;
run;
data group2est2;
  set group2est;
  GMFI=10**estimate;
  GMFI_LCL=10**LCLmean;
  GMFI_UCL=10**UCLMean;
  keep estimate lclmean uclmean GMFI:;
  label estimate='Mean Log10 Fold Increase'
    lclmean='Lower 95% CI of the Mean Log10 Fold Increase'
    uclmean='Upper 95% CI of the Mean Log10 Fold Increase'
    GMFI='Geometric Mean Fold Increase'
    GMFI_LCL='Lower 95% CI of the Geometric Mean Fold Increase'
    GMFI_UCL='Upper 95% CI of the Geometric Mean Fold Increase'
  ;
run;
```

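### SAP multiple-imputation sample code contradicts the SAP text: the Groups 2 and 3 floor is not on the log10 scale, and both VAR lists omit the endpoint to be imputed

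*SAP*

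**What the plan says.** SAP 4.2.3.2 describes a multiple-imputation sensitivity analysis on the Safety Analysis Set, run separately by group and only if data are missing. It gives a SAS program for Group 1 and another for Groups 2 and 3, the latter introduced as follows: "The following is the sample code for the MI sensitivity analyses of the primary estimand for Groups 2 and 3".

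**Floor.** For both programs the text sets a minimum of log10 of "half of the LLOQ will be set for imputed values to correspond to the observed data range". The Groups 2 and 3 code has "minimum=[LLOQ/2". The Group 1 code has "minimum=[log10LLOQ/2". The variable lists define every titre variable as a log10 result.

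**Variables.** In Groups 2 and 3 the VAR statement is "var stratgroup yob sex race ltiterBL ltiterW1", the imputation model is "fcs nbiter=20 reg(ltiterW2 = ltiterBL ltiterW1 stratgroup yob sex race", and the analysed quantity is "lfoldinc= ltiterW2 - ltiterBL". In Group 1 the VAR statement is "var nvacc yob sex race ltiterW2 ltiterW4 ltiterW5", while the FCS regression target and the variable passed to PROC MEANS are both ltiterW6.

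**Intent.** The text makes the Week 6 or Week 2 titre the variable to be predicted. It also requires a fold increase for every Safety Analysis Set subject in Groups 2 and 3.

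**The concern.** Each program departs from the method described beside it.

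A floor of LLOQ/2 on a log10 variable is a titre of 10 to the power LLOQ/2, not LLOQ/2. If applied, it forces imputed titres upward. A raised Week 2 value inflates the fold increase, and a raised baseline value deflates it.

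Leaving the endpoint out of VAR puts the purpose of the analysis at risk. SAP 1.1 includes this analysis to account for the whole trial population. If the endpoint is not imputed, the subjects it is meant to add drop out again. Apart from any imputed baselines, the result would then repeat the observed-value analysis of SAP 4.2.3.1.

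**Working it through.** **Inputs from SAP section 6:** SD 0.5 log10 before and after the booster, correlation 0.3, n = 90 per seropositive group, illustrative fold increase 4. **Assumed, because the documents give no value:** LLOQ 2, 5 or 10; baseline GMT 50 (range 20 to 100), so Week 2 GMT is 4 × 50 = 200; share of Week 2 values imputed 5% (range 2% to 10%).

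**1. The plan's own precision.** SD of the log10 difference = √(2 × 0.25 × 0.7) = 0.592. Half-width = 1.96 × 0.592/√90 = 0.122, and 4 × 10^(±0.122) gives 3.0 to 5.3. This matches the SAP.

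**2. Gap between the two floors.** With x = LLOQ/2, the gap on the log10 scale is x − log10(x). It is smallest at x = 1/ln 10 = 0.434, where it equals 0.797, or 6.26-fold. The coded floor therefore exceeds the text floor by at least that much at any LLOQ.

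| LLOQ (assumed) | Text floor as titre | Coded floor as titre | Chance a Week 2 draw clears the coded floor |
|---|---|---|---|
| 2 | 1 | 10 | 0.995 |
| 5 | 2.5 | 316 | 0.35 |
| 10 | 5 | 100,000 | 3e-8 |

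The last column is 1 − Φ(z), with z = (LLOQ/2 − log10 200)/0.5.

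**3. Effect on the fold increase if VAR is corrected and the coded floor kept.** The mean of a draw truncated at the floor is E = μ + 0.5 × φ(z)/(1 − Φ(z)). With μ = log10 200 = 2.301:
- LLOQ 2: E − μ = 0.007, so 4 × 10^(0.05 × 0.007) = 4.00.
- LLOQ 5: E − μ = 0.534, so 4 × 10^(0.05 × 0.534) = 4.25.
- At the text floor both are 4.00.

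Over baseline GMT 20 to 100 and 2% to 10% imputed, the ranges are 4.00 to 4.04 (LLOQ 2) and 4.06 to 4.86 (LLOQ 5). A simulated regression imputation at LLOQ 5 (n = 90, 5 Week 2 values missing, 400 runs, simulation error about 0.03) gave 4.31 with the coded floor and 3.97 with the text floor.

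If 2 of 90 baselines are imputed instead, with μ = log10 50, then 4 × 10^(−(2/90)(E − μ)) is 3.98 at LLOQ 2 and 3.80 at LLOQ 5.

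**4. Effect if the endpoint is not imputed.** With 5 of 90 Week 2 values missing, n = 85 and the half-width is 1.96 × 0.592/√85 = 0.126, against 0.122.

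**5. Group 1 placeholder.** It can be read as log10(LLOQ/2) or as log10(LLOQ)/2. As titres these are LLOQ/2 and √LLOQ: 1 and 1.41 at LLOQ 2, 2 and 2 at LLOQ 4, 2.5 and 2.24 at LLOQ 5, 5 and 3.16 at LLOQ 10, 10 and 4.47 at LLOQ 20. The readings differ by 1.0- to 2.2-fold, and no material effect is claimed.

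**The case against.** The best defence is that this is labelled sample code with a bracketed placeholder, next to prose that states the floor correctly for both programs and names the endpoint as the variable to predict. The FCS line also names the endpoint. A careful programmer would follow the text. If the step failed, the slip would show itself before any result was reported. The analysis runs only if data are missing, out-of-window titres are used before anything is imputed, and no hypothesis is tested.

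All of that stands, and it limits the weight of the point. It does not remove it. The SAP's introduction says that the document outlines the key programming specifications and will be followed completely, so code that conflicts with the prose should be corrected.

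A second objection is that the floor point rests on one absent token in a line where text extraction has visibly damaged spacing, so a lost log10 cannot be fully excluded. That is fair for the floor and can be settled by looking at the source document. The VAR omission is sturdier: both statements run complete to the semicolon and show the same gap. Differences in dataset names within the code may come from extraction and are not relied on.

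**Conclusion.** The concern holds, as a minor one. The Groups 2 and 3 code sets its floor on the wrong scale, and both programs leave the imputed endpoint out of VAR. Whether the omission makes the step fail or leaves the endpoint unimputed cannot be settled from the documents.

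Under the stated assumptions, every shifted estimate at LLOQ 2 to 5 (3.80 to 4.86 for a true value of 4) lies inside the planned interval. Loss of the imputed subjects costs little precision. From about LLOQ 10, almost no draw could meet the coded floor, so failure or plainly implausible titres are the likely outcomes and no fold increase is estimated there. The primary analysis (SAP 4.2.2), the observed-value Safety Analysis Set analysis (4.2.3.1) and the responder analyses (4.2.4) are untouched.

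**What to change.** In both programs, write the minimum explicitly as log10(LLOQ/2), with parentheses, and apply it to the titre variables only. Add ltiterW6 to the Group 1 VAR list and ltiterW2 to the Groups 2 and 3 list. Then test-run both programs on data with missing endpoint values and confirm that every Safety Analysis Set subject has a completed endpoint and that no imputed titre falls below LLOQ/2.

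The cost is an edit to the sample code and one test run. It needs no new data and no change of method. It is best done before the primary analysis of Groups 2 and 3, whose results SAP 4.6 treats as final.
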